4.1.2 Dose Escalation Phase (Part A)

The goal of the **Dose Escalation Phase (Part A)** is to initially characterize the safety and tolerability of margetuximab and pembrolizumab administered in combination, and more specifically to describe the DLTs for each dose level studied and to define the MTD or MAD (if no MTD is defined) based on the frequency of the occurrence of DLTs in each cohort during the **DLT Evaluation Period**.

For the purposes of guiding decisions regarding dose escalation, the **DLT Evaluation Period** is defined as the time following administration of the first dose of pembrolizumab up to the day of the second planned administration of pembrolizumab (i.e., 21 days following first dose of pembrolizumab - end of Cycle 1). DLTs are defined in **Section 4.2** and Dose Escalation Rules described in **Section 4.3**.

Margetuximab will be evaluated in two sequential escalating doses, 10 mg/kg and 15 mg/kg, in combination with 200 mg pembrolizumab in cohorts of 3 to 6 patients each. If it is determined that the MTD is exceeded in the first dose cohort, a dose de-escalation cohort to evaluate a lower dose of margetuximab (6 mg/kg) in combination with 200 mg pembrolizumab will be enrolled.

The dose escalation schema is outlined below:

Table 2 Margetuximab Dose Escalation Cohorts

Cohort	Margetuximab Dose	Pembrolizumab Dose
Cohort -1 ^a	6 mg/kg	200 mg
Cohort 1 ^b	10 mg/kg	200 mg
Cohort 2	15 mg/kg	200 mg

a To be evaluated only if the starting dose is determined to exceed the MTD.

b Starting dose level

An intermediate dose of margetuximab may be explored during the dose escalation portion of the study, based on review of the cumulative safety, efficacy, and/or PK data on the respective arms and based upon agreement between the investigators and the Sponsor. The Regulatory Agencies and Institutional Review Boards (IRBs)/Independent Ethics Committees (IECs) will be notified of any additional dose level to be evaluated.

4.1.3 Cohort Expansion Phase

4.1.3.1 Cohort Expansion Phase (Part B)

During Part B of the Cohort Expansion Phase, 60 patients (30 each in North America and Asia) with relapsed/refractory unresectable locally advanced or metastatic HER2+ GEJ or GC will be

enrolled under the Original Protocol and Protocol Amendment 1 to receive margetuximab at the RP2D established from the **Dose Escalation Phase (Part A)** of the study (15 mg/kg) in combination with 200 mg pembrolizumab. The goals for this portion of the study will be to:

1. Provide a preliminary assessment of the antitumor activity of margetuximab in combination with pembrolizumab in patients with relapsed/refractory unresectable locally advanced or metastatic HER2+ GEJ or GC.
2. Further characterize the safety of margetuximab in combination with pembrolizumab at the MTD (or MAD); and
3. Further evaluate the PK, PD, and immunogenicity of margetuximab in combination with pembrolizumab.

4.1.3.2 Cohort Expansion Phase (Part C)

During Part C of the Cohort Expansion Phase, up to 25 patients in North America and/or Asia with unresectable locally advanced or metastatic HER2+ (IHC 3+) GC will be enrolled under Protocol Amendment 2 (as further described in **Section 5.1**) to receive the same regimen of margetuximab in combination with pembrolizumab as described above. The goal for this portion of the study will be to:

1. Provide a preliminary assessment of the antitumor activity of margetuximab in combination with pembrolizumab in patients with relapsed/refractory unresectable locally advanced or metastatic HER2 3+ (IHC3+) GC only (as defined in AJCC Cancer Staging Manual, 8th Edition) post-trastuzumab
2. Further characterize the safety of margetuximab at the MTD (or MAD) in combination with pembrolizumab; and
3. Further evaluate the PK, PD, and immunogenicity of margetuximab in combination with pembrolizumab.

4.1.4 Efficacy Follow-up Period

Following a patient's final dose of study drug (pembrolizumab or margetuximab, whichever is last), each patient will be followed during the **Efficacy Follow up Period**. The **Efficacy Follow up Period** will end 3 months after the last patient completes or discontinues treatment. During this time, patients will be followed at 12-week intervals for monitoring of progression-free survival and overall survival. Disease assessments should be done at office follow-up visits if patients are agreeable.

Prior to database lock for final OS analysis, survival data will be requested for all patients still in **Efficacy Follow-up Period**, regardless of the interval since the prior assessment.

4.2 Dose Limiting Toxicity

For the purposes of safety management and defining DLTs, the combination of margetuximab and pembrolizumab will be treated as one entity during Cycle 1 of the **Dose Escalation Phase (Part A)** (i.e., the **DLT Evaluation Period**). If a DLT considered related to one of the study drugs occurs during this period, administration of both agents will be stopped. One exception to this rule will be in the circumstance in which a DLT occurs during or immediately following the first pembrolizumab infusion and before the first margetuximab administration. In this case, the toxicity will be attributed to pembrolizumab alone and will not count as a DLT of the combination of study drugs, and the patient will be replaced by another patient in the dose cohort.

In general, for patients who experience an AE that may meet the criteria for a DLT at any time during the course of the study, subsequent administration of the study drugs should be held pending management and/or resolution of the event and assessment of attribution to the study drugs. Criteria for subsequent continuation of therapy are outlined below. No intra-patient dose reductions of either margetuximab or pembrolizumab are allowed during the study.

4.2.1 Definitions

Dose limiting toxicities will be based on treatment-emergent drug-related AEs (or clinically significant laboratory abnormalities) occurring during the **DLT Evaluation Period** (defined as the time following administration of the first dose of pembrolizumab up to the day of the second planned administration of pembrolizumab [i.e., 21 days following first dose of pembrolizumab – end of Cycle 1]). The severity of AEs will be graded according to the National Cancer Institute (NCI) Common Terminology Criteria for Adverse Events (CTCAE) version 4.03.

Dose limiting toxicities are defined separately for hematologic and non-hematologic events as outlined below.

4.2.2 Hematologic Dose Limiting Toxicity

Hematologic DLT will be defined as follows:

- Grade 4 neutropenia lasting > 5 days
- \geq Grade 3 febrile neutropenia lasting > 48 hours or any \geq Grade 3 febrile neutropenia associated with hemodynamic compromise or objective evidence of infection
- Grade 4 thrombocytopenia, irrespective of duration
- Grade 3 thrombocytopenia associated with clinically significant bleeding
- \geq Grade 3 hemolysis

The following events will be specifically **excluded** from the definition of hematologic DLT:

- \geq Grade 3 lymphopenia
- Grade 3 anemia that is not associated with other clinically significant complications

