For the purposes of safety management and defining DLTs (limited to Cycle 1 of the Dose Escalation Phase [Part A]), the combination of margetuximab and pembrolizumab will be treated as one entity during Cycle 1 of the **Dose Escalation Phase (Part A)** (i.e., the **DLT Evaluation Period**). If a DLT is considered related to one of the study drugs during this period, administration of both agents will be stopped. One exception to this rule will be in the circumstance in which a DLT occurs during or immediately following the first pembrolizumab infusion and before the first margetuximab administration. In this case, the toxicity will be attributed to pembrolizumab alone and will not count as a DLT of the combination of study drugs and the patient will be replaced by another patient in the dose cohort.

In general, for patients who experience an adverse event (AE) that may meet the criteria for a DLT, subsequent administration of the study drugs should be held pending management and/or resolution of the event and assessment of attribution to the study drugs. Criteria for subsequent continuation of therapy are outlined below. No intra-patient dose reductions of either margetuximab or pembrolizumab are allowed during the study.

Definitions

Dose limiting toxicities will be based on treatment-emergent, drug-related AEs (or clinically significant laboratory abnormalities) occurring during the **DLT Evaluation Period** (defined as the time following administration of the first dose of pembrolizumab to the day of the second planned administration of pembrolizumab [i.e., 21 days following first dose of pembrolizumab – end of Cycle 1]). The severity of AEs will be graded according to the National Cancer Institute Common Terminology Criteria for Adverse Events v4.03 (NCI CTCAE v4.03).

Dose limiting toxicities are defined separately for hematologic and non-hematologic events as follows.

Hematologic Dose Limiting Toxicity

Hematologic DLT will be defined as follows:

- Grade 4 neutropenia lasting > 5 days
- \geq Grade 3 febrile neutropenia lasting > 48 hours or any \geq Grade 3 febrile neutropenia associated with hemodynamic compromise or objective evidence of infection
- Grade 4 thrombocytopenia, irrespective of duration
- Grade 3 thrombocytopenia associated with clinically significant bleeding
- \geq Grade 3 hemolysis

The following events will be specifically excluded from the definition of hematologic DLT:

- \geq Grade 3 lymphopenia

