Patients who receive treatment and who achieve an objective response status of stable disease (SD), unconfirmed partial response (uPR), confirmed partial response (cPR), unconfirmed complete response (uCR), confirmed complete response (cCR), or unconfirmed progressive disease (uPD) according to immune-related response criteria (irRC) at the Week 6 radiographic disease assessment will be eligible to receive subsequent cycles of treatment, assuming that they remain clinical stable and have not experienced DLTs that necessitate permanent discontinuation of study drugs. Radiographic disease assessments will occur every 6 weeks (i.e., following 2 cycles of treatment [specifically prior to Cycles 3, 5, 7 etc.]). Patients who have experienced PD as evidenced by $\geq 20\%$ increase in the dimensions of target lesions or the occurrence of new lesions may continue therapy at the discretion of the investigator pending confirmation of the PD at the next planned tumor assessment and satisfaction of criteria for irPD. Subsequent cycles of therapy after an initial documentation of PD should be administered to patients who have demonstrated

acceptable tolerance to treatment, who remain otherwise clinically stable, and who, in the assessment of the investigator, may derive clinical benefit from the continuation of treatment.

It is expected that enrollment of Part A of the study will occur over approximately 6 months, and enrollment of Parts B – C will take approximately 9 – 18 months.

The total time for conduct of the trial is expected to be approximately 60 months. These estimates of the timing for study conduct may vary from that observed in the actual conduct of the trial.

Treatment Schedule (Procedure): see Time and Events ([Appendix 1](#), and [Appendix 2](#)).

Criteria for Evaluation:

Safety Assessments:

- The safety assessment will be based on the evaluation of treatment-emergent AEs that occur from the time of initiation of administration of either study drug through the End of Treatment Visit, 28 days after the last dose of study drug, or the initiation of another anti-cancer treatment (whichever is later) and will be determined based on signs, symptoms, physical examination findings and/or laboratory test results from enrolled patients as appropriate

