4.2.3 Non-Hematologic Dose Limiting Toxicity

Non-hepatic non-hematologic DLT will be defined as any \geq Grade 3 non-hematologic event **with the following exceptions**:

- Grade 3 electrolyte abnormality that lasts less than 72 hours, is not otherwise associated with clinical complications, and responds to medical intervention
- Grade 3 fever that lasts $<$ 72 hours and is not associated with hemodynamic compromise
- Grade 3 nausea or vomiting that lasts $<$ 72 hours and responds to medical intervention
- Grade 3 or 4 amylase and/or lipase elevation that is not associated with either clinical or radiographic evidence suggestive of pancreatitis
- Grade 3 diarrhea that lasts $<$ 48 hours and responds to medical intervention
- Grade 3 gastrointestinal AEs of constipation, abdominal pain, cramping, dyspepsia or dysphagia that resolves to \leq Grade 1 within 14 days with medical therapy
- Grade 3 fatigue that lasts $<$ 7 days
- Grade 3 infusion-related reaction or cytokine release syndrome that lasts $<$ 12 hours and responds to medical intervention.
- Grade 3 or 4 endocrinopathy that is adequately controlled with hormone supplementation
- Grade 3 skin toxicity that resolves to \leq Grade 2 within 14 days of initiation of oral corticosteroids
- Grade 3 inflammatory reaction (e.g., with associated pain, swelling) attributed to a local antitumor response (e.g., inflammatory reaction at sites of metastatic disease, lymph nodes, etc.) that resolves to \leq Grade 2 within 7 days with medical intervention

Note: The following Grade 2 or greater non-hematologic AE may also be considered as DLT:

- Grade 2 AEs that are prolonged inordinately, based upon the medical judgment of the investigator, and/or lead to permanent discontinuation of study drug(s) due to patient intolerance.
- Any \geq Grade 2 drug-related AE that results in $>$ 7-day treatment delay would be considered a DLT.

- Any hepatic laboratory abnormalities meeting all three Hy's law criteria (described within **Section 4.2.4** below).
- Any Grade 2 eye pain or reduction in visual acuity that does not respond to topical therapy and does not improve to Grade 1 within 14 days of the initiation of topical therapy, or that requires systemic treatment.

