6.5.2.9 Other Immune-Related AEs

- Intolerable/persistent Grade 2
 - Hold pembrolizumab and margetuximab
 - Based on the type and severity of AE, administer corticosteroids
 - Ensure adequate evaluation to confirm etiology and/or exclude other causes

- Grade 3
 - Hold or discontinue pembrolizumab and margetuximab based on the type of event
 - Discontinuation is required for AEs such as, but not limited to, Guillain-Barré Syndrome and encephalitis
 - Recurrence of the same Grade 3 toxicity requires discontinuation
- Grade 4
 - Permanently discontinue

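### The closed hematologic DLT list omits non-hemolytic anemia, while the exclusion exempts only uncomplicated Grade 3 anemia, so Grade 4 and complicated Grade 3 anemia are neither DLTs nor excluded

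*Protocol*

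**What the plan says.** Protocol 4.2.2 gives five hematologic DLTs: Grade 4 neutropenia beyond 5 days; specified febrile neutropenia; Grade 4 thrombocytopenia of any duration; Grade 3 thrombocytopenia with clinically significant bleeding; and hemolysis of Grade 3 or worse. It then takes two events out of the definition. One is lymphopenia at or above the level "Grade 3 lymphopenia". The other is "Grade 3 anemia that is not associated with other clinically significant complications". The synopsis repeats both lists. The SAP contains no DLT definition.

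The protocol gives two signals on when DLT criteria apply.

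- **Cycle 1 only.** The synopsis opens its DLT text with "For the purposes of safety management and defining DLTs (limited to Cycle 1 of the Dose Escalation Phase [Part A" (closing brackets cut here). Section 4.2.1 bases DLTs on events in the 21-day evaluation period.
- **Any time.** Section 4.2 sets a hold rule "for patients who experience an AE that may meet the criteria for a DLT at any time during the course of the study". Sections 4.4 and 4.5 stop treatment for a drug-related DLT and name no cycle. The synopsis, under Duration of Treatment, lets patients continue after the Week 6 scan if they "have not experienced DLTs that necessitate permanent discontinuation of study drugs".

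**The concern.** An exclusion limited to Grade 3 anemia without complications does useful work only if worse anemia would otherwise count. Under a closed list without anemia, nothing would otherwise count. The list and the exclusion therefore imply different rules for the same event.

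DLTs and the MTD or MAD belong to the first primary objective (Protocol 3.1, SAP 2.1). Anemia is also a plausible toxicity here: Protocol 2.3.2.1 names it first among the most common Grade 3-5 drug-related events on pembrolizumab alone. Two sites or two analysts could classify the same Cycle 1 event differently. If DLT criteria also govern later cycles, one patient could be restarted under one reading and withdrawn under the other.

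**Working it through.** The plan states no figure on this point, so the check is mainly a comparison of texts.

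1. **Is the list closed?** Yes. Section 4.2.2 defines hematologic DLT by its items, with no opening for other events. The only red-cell item is hemolysis.

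2. **Does another DLT rule reach anemia?** Section 4.2.1 says hematologic and non-hematologic DLTs are defined separately. The Grade 3 or worse default in 4.2.3 covers non-hematologic events only. One bullet there counts any drug-related event of Grade 2 or worse that delays treatment by more than 7 days. Its lead-in, however, is "Note: The following Grade 2 or greater non-hematologic AE may also be considered as DLT", so its reach to anemia is doubtful.

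3. **What does the exclusion imply?**
   - Lymphopenia is exempt at Grade 3 and above. Anemia is exempt only at Grade 3 and only without complications.
   - Thrombocytopenia counts at Grade 4, or at Grade 3 with bleeding. The anemia exclusion leaves the matching pair unaddressed: Grade 4, or Grade 3 with complications.
   - On the other side, lymphopenia is excluded without being listed, so an exclusion alone does not prove that the event was otherwise meant to count.

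   Intent is therefore likely, not certain.

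4. **What is left in the gap?** Remove hemolysis of Grade 3 or worse (listed) and drug-related complications that are DLTs themselves under 4.2.3. Immune-related anemia stays outside the DLT list, but 6.5.2.9 governs its treatment: at Grade 4, "Permanently discontinue"; at Grade 3, "Recurrence of the same Grade 3 toxicity requires discontinuation". What stays wholly unaddressed is drug-related, non-hemolytic, non-immune anemia of Grade 4, or of Grade 3 with complications that are not DLTs.

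5. **Where does the label still matter?**
   - *Part A count.* Such an event would appear in the table of treatment-related events of Grade 3 or worse (SAP 6.7.1) but would not be labelled a DLT.
   - *Patients on treatment.* Under 4.5.1, a toxicity that is not a DLT may be followed by restart at the same dose once it is Grade 1 or lower. A related delay above 14 days ends treatment. Section 6.8 permits red-cell transfusion, which can speed that recovery. Under 4.4 and 4.5, a drug-related DLT ends treatment.

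6. **Size on the dose scale.** Section 4.3 reports 6 patients at the recommended dose and sets the limit at 2 of 6. One event is 1/6 = 16.7%; two are 2/6 = 33.3%. One reclassified event takes 0/6 to 1/6, which changes no decision, or 1/6 to 2/6, which is the limit. The documents report neither the Part A DLT count nor an anemia rate, so the chance of either cannot be derived.

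**The case against.** The strongest reply is that this is a drafting point in a finished phase. Section 4.2.1 and the synopsis confine DLTs to Cycle 1 of dose escalation, and the Part A dose is settled at 15 mg/kg (2.5.2). Other controls cover much of the gap:

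- 4.4 allows withdrawal for an adverse event or at the investigator's discretion;
- 4.5.1 requires recovery to Grade 1 or lower and stops treatment after 14 days of related delay;
- 7.9.4 has every Grade 4 value assessed for seriousness;
- 7.9.5.1 has Grade 3 and 4 laboratory findings reported as adverse events;
- 4.3 required safety review before escalation.

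Most of this stands, and it limits the consequence. It does not remove the conflict between list and exclusion. The controls in 4.4 and 4.5.1 leave restart or withdrawal to judgement, whereas a DLT requires withdrawal. The Cycle 1 limit also does not settle later handling, because 4.2, 4.4 and 4.5 use DLT criteria without repeating it.

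A reader might infer two stronger claims that the documents do not support. The first is that the recommended dose was wrongly chosen. That would need a reclassifiable anemia and an existing count of 1/6, and neither is reported; Section 2.3.1.1 describes margetuximab as tolerable with no safety signal of concern. The second is that a patient in Part B or C with such an anemia must be withdrawn under the intended reading. That also requires a later-cycle event to qualify as a DLT, which 4.2.1 contradicts.

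**Conclusion.** The gap is real and appears in both 4.2.2 and the synopsis. Read literally, drug-related Grade 4 anemia and complicated Grade 3 anemia, if non-hemolytic, fall outside both the DLT list and its exclusions, which most likely contradicts the intent. No dose decision, sample size or efficacy analysis changes.

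Two effects remain: the reported Part A DLT count, in steps of 16.7 percentage points for the 6 patients at the recommended dose, and the handling of patients on treatment, to the extent that DLT criteria apply after Cycle 1. The number of patients affected cannot be derived from the documents and may be zero. The conclusion rests on reading the list as closed and on inferring intent from the narrowness of the exclusion. The point deserves correction at the next amendment because it touches a primary safety objective and the correction is small.

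**What to change.** Add to the hematologic list in 4.2.2 and the synopsis: *Grade 4 anemia, or Grade 3 anemia associated with clinically significant complications*. That line alone would not help current patients, because 4.2.1 still limits DLTs to Cycle 1. So also state in 4.4, 4.5 and 4.5.1 that events meeting these severity criteria are handled the same way in any cycle and any part, whether or not they carry the DLT label.

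For Part A, keep the original classification, check Cycle 1 drug-related anemias against the corrected list, and report the DLT count both ways if any event is affected. If the sponsor never meant these anemias to count, the alternative is to exclude all non-hemolytic anemia openly, as is done for lymphopenia.

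The cost is one line in two places, a sentence in three sections, and a review of anemias in a phase planned for up to 12 patients before replacements. The DLT count could become slightly less favourable, and a patient with quickly reversible Grade 4 anemia would be withdrawn where restart is now possible.

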4.2.3 Non-Hematologic Dose Limiting Toxicity

Non-hepatic non-hematologic DLT will be defined as any \geq Grade 3 non-hematologic event **with the following exceptions**:

- Grade 3 electrolyte abnormality that lasts less than 72 hours, is not otherwise associated with clinical complications, and responds to medical intervention
- Grade 3 fever that lasts $<$ 72 hours and is not associated with hemodynamic compromise
- Grade 3 nausea or vomiting that lasts $<$ 72 hours and responds to medical intervention
- Grade 3 or 4 amylase and/or lipase elevation that is not associated with either clinical or radiographic evidence suggestive of pancreatitis
- Grade 3 diarrhea that lasts $<$ 48 hours and responds to medical intervention
- Grade 3 gastrointestinal AEs of constipation, abdominal pain, cramping, dyspepsia or dysphagia that resolves to \leq Grade 1 within 14 days with medical therapy
- Grade 3 fatigue that lasts $<$ 7 days
- Grade 3 infusion-related reaction or cytokine release syndrome that lasts $<$ 12 hours and responds to medical intervention.
- Grade 3 or 4 endocrinopathy that is adequately controlled with hormone supplementation
- Grade 3 skin toxicity that resolves to \leq Grade 2 within 14 days of initiation of oral corticosteroids
- Grade 3 inflammatory reaction (e.g., with associated pain, swelling) attributed to a local antitumor response (e.g., inflammatory reaction at sites of metastatic disease, lymph nodes, etc.) that resolves to \leq Grade 2 within 7 days with medical intervention

Note: The following Grade 2 or greater non-hematologic AE may also be considered as DLT:

- Grade 2 AEs that are prolonged inordinately, based upon the medical judgment of the investigator, and/or lead to permanent discontinuation of study drug(s) due to patient intolerance.
- Any \geq Grade 2 drug-related AE that results in $>$ 7-day treatment delay would be considered a DLT.

- Any hepatic laboratory abnormalities meeting all three Hy's law criteria (described within **Section 4.2.4** below).
- Any Grade 2 eye pain or reduction in visual acuity that does not respond to topical therapy and does not improve to Grade 1 within 14 days of the initiation of topical therapy, or that requires systemic treatment.

